8.3 Data Monitoring Board

An external and independent Data Safety Monitoring Board (DSMB) will be instituted before study start. The DSMB will review safety-related issues and will be entitled to make recommendations for changes in study conduct. Details on the function of the DSMB will be laid out in a separate DSMB Charter.

9 Data review and database management

9.1 Site monitoring

Before study initiation, at a site initiation visit or at an investigator's meeting, a Novartis representative will review the protocol and CRFs with the investigators and their staff. During the study, the field monitor will visit the site regularly to check the completeness of patient records, the accuracy of entries on the CRFs, the adherence to the protocol and to Good Clinical Practice, the progress of enrollment, and to ensure that study drug is being stored, dispensed, and accounted for according to specifications. Key trial personnel must be available to assist the field monitor during these visits.

The investigator must maintain source documents for each patient in the study, consisting of case and visit notes (hospital or clinic medical records) containing

demographic and medical information, laboratory data, electrocardiograms, and the results of any other tests or assessments. All information on CRFs must be traceable to these source documents in the patient's file. Data not requiring a written or electronic record will be defined before study start and will be recorded directly on the CRFs, which will be documented as being the source data. The investigator must also keep a copy of the signed informed consent form.

The investigator must give the monitor access to all relevant source documents to confirm their consistency with the CRF entries. Novartis monitoring standards require full verification for the presence of informed consent, adherence to the inclusion/exclusion criteria, documentation of SAEs, and the recording of data that will be used for all primary efficacy and safety variables. Additional checks of the consistency of the source data with the CRFs are performed according to the study-specific monitoring plan. No information in source documents about the identity of the subjects will be disclosed.

9.2 Data collection

Designated investigator staff must enter the information required by the protocol onto the Novartis CRFs that are printed on 3-part, non-carbon-required paper. Field monitors will review the CRFs for completeness and accuracy and instruct site personnel to make any required corrections or additions. The CRFs are forwarded to Data Management by field monitors or by the investigational site, one copy being retained at the investigational site and one copy being the working copy for the monitor. Once the CRFs have been received by Data Management, their receipt is recorded and forwarded for data entry and data management processes. If CRFs have been sent for data entry by the investigational site directly, Data Management staff has to review the CRFs upon receipt for any serious adverse event.

9.3 Database management and quality control

Data from the CRFs are entered into the study database by Contract Research Organization staff using double data entry with verification upon second entry. Text items (e.g. comments) are entered once and checked manually against the CRF.

Subsequently, the entered data are systematically checked by Data Management staff, using error messages printed from validation programs and database listings. Obvious errors are corrected by Data Management personnel, according the obvious correction document. Other errors or omissions are entered on Data Query Forms, which are returned to the investigational site for resolution. The signed original and resolved Data Query Forms are kept with the CRFs at the investigator site, and a copy is sent Data Management so the resolutions can be entered into the database. Quality control audits of all key safety and efficacy data in the database are made prior to locking the database.

Concomitant medications entered into the database will be coded using the WHO Drug Reference List, which employs the Anatomical Therapeutic Chemical classification system. Medical history/current medical conditions and adverse events

will be coded using the Medical dictionary for regulatory activities (MedDRA) terminology.

At the conclusion of the study, the occurrence of any protocol violations will be determined. After these actions have been completed and the database has been declared to be complete and accurate, it will be locked and made available for data analysis. Any changes to the database after that time can only be made by joint agreement between the Trial Statistician and the Clinical Trial Leader (both from the German CPO).

10 Statistical methods

10.1 Statistical methods

Analyses will be done when all patients have completed the trial at 18 months post Tx (or discontinued prematurely). The following periods will be considered for analyses:

- The primary analysis of renal safety and tolerability concerns the period of randomized treatment between Month 6 (baseline) and Month 18 or the last assessment within this period in the event of a patient's premature discontinuation from the study. If indicated, e.g. for analysis of renal function and type and frequency of adverse events, the period from Month 6 to Month 18 may be portioned into (a) the switch period between Month 6 and Month 9 and (b) the maintenance period between Months 9 and 18 after Tx.
- As a separate study period, the first 6 months between transplantation and Month 6 post Tx will be analyzed with regard to treatment, efficacy, and safety of the immunosuppressive regimen.
- To allow conclusions about the total treatment period of the CNI-based versus the CNI-free treatment regimen including initial treatment and randomized therapy, the total period between transplantation and Month 18 will be analyzed and compared between the two treatment groups. In patients who discontinue prematurely from the study, both the last available information under study treatment as well as an additional assessment at Month 18 will be analyzed.

The group of patients who were not randomized to one of the two treatment groups at Month 6 (Baseline visit) will be handled as a third patient group within exploratory analyses and described with respect to primary and secondary outcome variables and treatment variables for the same periods as described above.

Adverse events will be analyzed separately for the initial 3 months period between Screening and Baseline visit and for the randomized treatment period between Baseline visit (Month 6) and Month 18, but also for the total treatment period.

Significant events like rejection episodes, hemodynamic compromise, and MACE will additionally be analyzed for the period between transplantation and Screening (Month 3 post Tx).

Unless otherwise stated, all statistical tests will be two-sided and use the 0.05 level of statistical significance. All summary statistics will be presented by treatment group. Frequency distributions will be provided for categorical variables and the two treatment groups will be compared with chi²-tests. Descriptive statistics of mean, standard deviation, minimum, median and maximum will be presented for continuous variables, comparisons of the two treatment groups will be performed with suitable chosen 2-sample tests. Time to event data including rates of affected patients will be assessed by Kaplan-Meier statistics and compared between the two groups with the logrank test.

Data from all centers that participate in this study will be combined.

A detailed description of the statistical evaluation of this study will be provided in a Statistical Analysis Plan which will be finalized prior to closure of the study database.

10.2 Populations for analysis

The enrolled patient population (ENR population) will include all patients who signed an informed consent regardless whether they received study treatment or not.

The Safety Population (SAF population) will consist of all patients who signed an informed consent and who were treated with at least one dose of any immunosuppressive medication after the Screening visit.

Note: The statement that a patient had no adverse events constitutes a safety assessment.

The Randomized Population (RAN) is defined by all patients who were randomized at Baseline visit. This population will include patients who were randomized but not treated with the randomized medication.

The ITT population will consist of all randomized patients who received at least one dose of any immunosuppressive therapy after Baseline Visit (Month 6) and have at least one post-baseline assessment of the primary outcome variable (renal function based on MDRD method). Randomized patients without data on the primary outcome variable will be excluded from this population; their data will be analyzed for the initial treatment period (up to Month 6) and within the RAN and SAF.

Following the intent-to-treat principle, patients will be analyzed according to the treatment group they were assigned to at randomization.

The Per-protocol Population will consist of all ITT patients who did not show major deviations from the protocol procedures that may have an impact on the study outcome and who have completed the treatment phase at Month 18 according to protocol. Criteria that are assumed to have such an impact will be defined before analysis during the Blind Review Meeting.

Besides the two patient groups who were eligible for randomization, a third patient group will be defined in whom a heart transplantation was performed but who did not qualify for randomization at Baseline visit (Month 6). This group will be addressed as "not randomized patients" (NRP) and described with respect to treatment and outcome variables.

10.3 Background and demographic characteristics

Demographic and background information will be summarized for the ENR-, the SAF-, the ITT-, and the PP- Population, using frequency distributions for categorical variables and descriptive statistics of mean, standard deviation, minimum, median and maximum for continuous variables. Background information includes prior medication, past/current medical conditions and transplant history.

Medical history will be coded using MedDRA and will be presented by system organ class, MedDRA preferred term and treatment group. Separate tables will be provided for past medical condition and current medical condition. Prior medication will be coded according to WHO Drug Reference List.

In addition to these variables which were evaluated at Screening (Visit 1, Month 3 post Tx), the course of renal function (GFR) as well as efficacy variables (treated acute rejection, biopsy proven acute rejection of ISHLT 1990 grade \geq 3A resp. ISHLT 2004 grade \geq 2R, acute rejection associated with hemodynamic compromise, graft loss / re-transplantation, death) will be determined and properly described for the period between Transplantation and Baseline (Visits 2 - Month 6 post Tx).

The two treatment groups will be compared descriptively with respect to these variables. Further, the NRP group will be described using the same variables.

No formal statistical testing is planned for comparability purposes.

10.4 Study treatments

10.4.1 Study medication

Study medication is Everolimus, RAD001); the other components of the immunosuppressive regimens are considered as concomitant medication.

Duration (days) of Everolimus, study medication application will be summarized. Dosage averages will be calculated including and excluding zero doses for periods of temporary interruption of study medication regardless of whether this was due to safety reasons or patients' non-compliance. Daily Everolimus, dose levels will be summarized with mean, standard deviation, minimum, median, and maximum by time interval. Frequency of dose reduction (including temporary dose interruption) for safety reasons as per protocol guidelines as well as average daily dose will be presented by visit. Reasons for dose adjustments (including temporary dose

interruption) will be presented by frequency distribution. Permanent treatment discontinuations will be analyzed by frequencies.

These analyses will be performed per treatment group, for the ITT- and the PP population and related to the study phases (see [section 10.1](#)).

10.4.2 Concomitant therapy

Daily Cyclosporin A and Tacrolimus doses adjusted by the patients' visit-specific body weight, MPA doses, and steroids (expressed in doses equivalent to prednisone) will be summarized by visit and in the same way as the study medication. Data will be presented separately for each treatment group. Induction therapy (Basiliximab or ATG or no induction) received by patient will be summarized by treatment group, for the total (SAF) population, but also for the NRP group.

Duration (days) of treatment with Cyclosporin A, Tacrolimus, MPA, and steroids as well as frequency of Cyclosporin A, Tacrolimus and MPA dose adjustments (including temporary dose interruption) for safety reasons as per protocol guidelines will be determined. Reasons for dose adjustments (including temporary dose interruption) will be presented by frequency distribution. Permanent treatment discontinuations will be analyzed using frequency distribution. All other immunosuppressive therapies will be summarized by ATC (Anatomical, Therapeutic, Chemical) classes.

All analyses for concomitant medication will be presented per treatment group and study phase (see [section 10.1](#)).

Corresponding data of the NRP group will be reported in a similar way.

Medications other than those mentioned in this section taken concomitantly with the study medication will be summarized by treatment group and study period through frequency tables. Concomitant medication will be coded and summarized according to the ATC classification system.

10.5 Primary objective

The primary aim of this study is to show superior renal function under the CNI-free regimen compared to the CNI-based regimen with respect to GFR as calculated by MDRD method.

10.5.1 Variable

The primary variable for assessment of renal function is the

- glomerular filtration rate (GFR) at Month 18, as assessed by the MDRD method (recalculated values, see [section 7.5](#)).

10.5.2 Statistical hypothesis, model, and method of analysis

According to the recommendation given in the Points to Consider document on “Adjustment for Baseline Covariates” (CPMP, 2003), the null hypothesis H_0 of similar GFR level in both treatment groups

$$H_0: \mu_{\text{CNI-free}} = \mu_{\text{CNI-based}}$$

will be tested against the two-sided alternative hypothesis of different efficacy (different GFR levels at month 18 after Tx) of the CNI-free regimen compared to the CNI-based regimen

$$H_1: \mu_{\text{CNI-free}} \neq \mu_{\text{CNI-based}}$$

with an analysis of covariance (ANCOVA) using “treatment” and “center” as factors and “baseline GFR value at Baseline visit 2 (Month 6)” as covariate. Type-I error probability will be set to a two-sided $\alpha=0.05$. Adjusted means (=LS-means, LS: least square means) will be presented for the treatment contrast of GFR at Month 18 post Tx together with its confidence interval and a two-sided p-value.

The ITT population will be used for the primary analysis. This analysis follows the intention-to-treat principle and thus reflects the actual performance of the investigational drug under practical conditions (“pragmatic approach”).

10.5.3 Handling of missing values/censoring/discontinuations with respect to the primary outcome variable

If a patient discontinues from the study prematurely missing data with respect to the target parameter will be substituted by the last recorded value (last observation carried forward, LOCF). The LOCF method will only be applied if a patient has at least one assessment after Baseline, i.e. on Visits Months 8 to 18. Otherwise, the patient will be excluded from efficacy analysis within the ITT population (see [section 10.2](#)). Under the assumption that the GFR will remain fairly stable or even worsen in the CNI group but will probably even improve in the CNI-free group, this strategy corresponds to a conservative estimate of the therapy effect within both treatment groups.

Additionally, sensitivity analyses will be performed including the following imputation strategy:

- Missing data for the primary outcome variable will be replaced by the mean of the non-missing values in the same treatment group. Further sensitivity analyses may be specified in the statistical analysis plan.

10.5.4 Supportive analyses

The course of the GFR will be of special interest. Changes from Baseline to each post-baseline measure will be calculated by treatment group for each study visit. In addition, the GFR as recalculated by the Cockcroft-Gault method will be analyzed in the same manner (see secondary objectives).

In addition to quantitative analyses, the frequency distributions of patients with an improved GFR at study month 18 compared to BL (Month 6 post Tx) will be compared between the two regimens.

If patients of the ITT population are switched from the CNI group to the CNI-free group during the study or during follow-up, they will be analyzed in their randomized group. If appropriate, a subgroup analysis will be performed comparing patients of the CNI group with and without switch to CNI-free treatment including a further analysis comparing both subgroups to the randomized CNI-free group. If treatment will be modified in the CNI-free group, they will be analyzed as randomized.

It is planned to evaluate renal function and efficacy variables also at Month 18 in patients who discontinue prematurely (prior to Month 18) from the trial. An additional exploratory analysis will be conducted using the assessments at Month 18.

Additionally to the analyses of data from the interval between BL (Month 6) and Month 18, the primary outcome variable will also be evaluated for the interval between Transplantation (prior to Tx) and Month 18.

Results from these supportive analyses will be interpreted in an explorative manner.

Corresponding data from the NRP group will be described in a similar manner.

10.6 Secondary objectives

10.6.1 Efficacy

The following secondary efficacy variables will be analyzed in an explorative manner:

- Occurrence of treatment failure up to Month 18 defined as composite endpoint of biopsy proven acute rejection of ISHLT 1990 grade \geq 3A resp. ISHLT 2004 grade \geq 2R, acute rejection episodes associated with hemodynamic compromise, graft loss / re-transplant, death, loss to follow up (at least one condition must be present).
- Occurrence of MACE and each of its components at Month 18

Additionally to the analyses of data from the interval between BL (Month 6 post Tx) and Month 18, all secondary outcome criteria will also be evaluated for the interval between Month 0 (prior to Tx) and Month 18.

Event data:

Event rates will be estimated using the Kaplan-Meier method to handle patients who discontinue the treatment prior to suffering from an event adequately. The two groups will be compared using the logrank test.

This procedure will be applied for the composite endpoint of treatment failure and each of its components, as well as MACE and each of its components.

Narratives including relevant medical information will be provided for each biopsy proven acute rejection, CAV, graft loss, or death.

Corresponding data from the NRP group will be described in a similar manner.

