#### **2.6.2      Statistical hypothesis, model, and method of analysis**

Event data:

Event rates were estimated using the Kaplan-Meier method to handle patients who discontinue the treatment prior to suffering from an event adequately. Time to event was defined as the time from date of randomization to the first documented date of the event. The two groups were compared using the log-rank test.

This procedure was applied for the composite endpoint of treatment failure and each of its components, as well as MACE and each of its components.

Narratives including relevant medical information were provided for each biopsy proven acute rejection, graft loss, or death.

Tolerability:

Analyses of renal function as determined by other calculations (serum creatinine, glomerular filtration rate (GFR, Cockcroft-Gault)) were evaluated in the same manner as described for the primary outcome measure.

The creatinine slope (1 / serum creatinine versus time) was determined from all assessments between Month 6 and Month 18 (both visits included) using a linear regression model. These slopes were compared with a two-sided Wilcoxon ranksum test between the treatment groups.

Additionally, tolerability of study medication was assessed from the rate of patients who withdraw prematurely from study medication or in whom study medication had to be converted to another immunosuppressive regimen due to abnormal laboratory results, adverse events, or toxicity. The frequency distribution of these reasons was presented with absolute and percent values. The most frequent reasons (total  $n \geq 5$ ) for discontinuation and/or conversion as well as the total number of patients who are affected by such intolerance of study medication were compared between the two treatment groups using the exact Fisher test.

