### **2.6.3 Handling of missing values/censoring/discontinuations**

Missing values were imputed with the last observation carried forward (LOCF) method described at section 2.5.3.

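### Kaplan-Meier rates for the non-fatal components of treatment failure and MACE overstate, slightly, the proportion of patients affected if deaths are censored; the plan states no rule for death

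*Protocol*

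**What the plan says.** Protocol 10.6.1 gives one estimator for all event data, and its reason concerns stopping treatment: "Event rates will be estimated using the Kaplan-Meier method to handle patients who discontinue the treatment prior to suffering from an event adequately". For the comparison it adds that "The two groups will be compared using the logrank test". Both are to be "applied for the composite endpoint of treatment failure and each of its components, as well as MACE and each of its components".

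SAP 2.6.2 keeps this rule. It states that "Event rates were estimated using the Kaplan-Meier method", that the "procedure was applied for the composite endpoint of treatment failure and each of its components, as well as MACE and each of its components", and it fixes the time origin: "Time to event was defined as the time from date of randomization to the first documented date of the event". Randomization is at Month 6, so follow-up to Month 18 is about 12 months.

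The components of treatment failure are biopsy-proven rejection, rejection with hemodynamic compromise, graft loss or re-transplantation, death and loss to follow-up. Those of MACE are any death, myocardial infarction and bypass grafting.

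The heading of SAP 2.6.3 mentions censoring, but the section contains only this: "Missing values were imputed with the last observation carried forward (LOCF) method described at section 2.5.3". That rule is for a repeatedly measured value such as GFR and does not say when a time-to-event record ends. SAP section 4, on changes to the protocol analyses, is silent on the matter. Neither document mentions competing risks or cumulative incidence.

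Protocol 10.6.1 and SAP 2.6.1 both class these analyses as explorative.

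**The concern.** A patient who stops treatment can still have a rejection or an infarction and is meant to be seen again at Month 18 (Protocol 6.5.5 and 7.1). A patient who has died cannot. Censoring both in the same way assumes that the dead patient would have gone on to have events at the same rate as those still followed. The resulting 1 minus Kaplan-Meier (1-KM below) describes a setting without deaths, and it exceeds the proportion actually affected whenever deaths occur before later events.

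The component rates will be read. Protocol sections 1 and 11 expect the CNI-free regimen to match the CNI regimen on rejection, graft loss and death, and Protocol section 3 makes each MACE component a secondary objective. A reader will take a reported 12-month rejection rate as the share of patients who had a rejection.

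**Working it through.** **Figures in the plan.** There is none to reproduce on this point. The sample size rests on GFR alone, and no component rate or death rate is given. The rates below are therefore assumptions, shown as a range.

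**Inputs from the documents.** 162 patients randomized 1:1 (SAP 1.1), so about 81 per arm; 12 months of follow-up from randomization.

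**Assumptions.** Constant cause-specific hazards over the 12 months, deaths censored, and death as the only competing event.

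**Formula.** Let k be the 12-month 1-KM value of the component and d the 12-month death probability. With l1 = -ln(1-k) and l2 = -ln(1-d), the proportion actually affected is

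CIF = l1/(l1+l2) × [1 - exp(-(l1+l2))], and the overstatement is k - CIF.

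**Worked case, k = 15%, d = 5%.** l1 = 0.1625 and l2 = 0.0513. The bracket is 1 - 0.85 × 0.95 = 0.1925. CIF = 0.1625/0.2138 × 0.1925 = 14.63%. The overstatement is 0.37 points, or 0.30 of a patient in 81.

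**Range: overstatement in percentage points**

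| 1-KM | d = 1% | d = 2% | d = 5% | d = 10% |
|---|---|---|---|---|
| 5% | 0.02 | 0.05 | 0.12 | 0.25 |
| 10% | 0.05 | 0.10 | 0.25 | 0.50 |
| 15% | 0.07 | 0.15 | 0.37 | 0.74 |
| 20% | 0.10 | 0.19 | 0.49 | 0.98 |
| 30% | 0.14 | 0.28 | 0.71 | 1.44 |

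Relative to the CIF, the overstatement is about 0.5%, 1%, 2.5% and 5% across the four columns, almost regardless of the event rate. In relative terms it follows mortality; in points it depends on the event rate as well.

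**Timing.** If every death fell just after randomization, the overstatement would reach its upper limit k × d: 0.75 points at 15% and 5%, and 3.0 points at 30% and 10%.

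**Starting from the true proportion.** Let B be the proportion with rejection and D the proportion dying without prior rejection. The rejection hazard is -ln(1-B-D) × B/(B+D), and 1-KM = 1 - exp(-rejection hazard).
- B = 20%, D = 5%: 20.6%
- B = 20%, D = 10%: 21.2%
- B = 30%, D = 10%: 31.8%, an overstatement of 1.8 points. This is above the table's maximum because here 30% is the true proportion and D counts only deaths before rejection.

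**Sampling error.** The 95% half-width for a 15% rate in 81 patients is 1.96 × √(0.15 × 0.85/81) = 7.8 points.

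**Log-rank test.** In 20,000 simulated trials of 81 per arm with equal rejection hazards (15% at 12 months) and deaths of 2% v 10%, the two-sided 5% test rejected in 5.1%. Unequal mortality does not distort it as a test of cause-specific hazards.

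**The case against.** The strongest reply is that this is a choice of what to estimate. Suppose the true proportions with rejection are equal at 20% and deaths without prior rejection are 3% v 10%. Then 1-KM shows a gap of 0.8 points (1.3 points at 30% rejection), and a reader might infer that Kaplan-Meier creates a false difference between arms. But equal proportions with unequal deaths imply unequal rejection hazards, 0.2273 v 0.2378, and Kaplan-Meier reflects them. In the reverse case, with 1-KM of 20% in both arms and 12-month deaths of 3% v 10%, cumulative incidence is 19.7% v 19.0%, which favors the arm with more deaths. The gap is false only if the proportion affected is the target. This part of the reply stands.

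Three other strong readings are not supported:
- **The arm with more deaths is always inflated more.** This holds in relative terms or at equal event rates. In points it can reverse: 0.28 for 30% rejection with 2% deaths, against 0.25 for 10% rejection with 5% deaths.
- **Kaplan-Meier is why the components do not add up to the composite.** They overlap. SAP 5.1.3 takes both rejection components from the same biopsy form and date, and a patient can have a rejection and later die. They need not add up under any estimator.
- **Graft loss ends the risk of infarction or bypass.** The documents do not say so, and follow-up runs to Month 18 (Protocol 7.1). Even for rejection, Protocol 7.5 dates graft loss to the scheduling of re-transplantation and SAP 5.1.3 to a hospital admission, when the original graft may still be in place.

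It is also fair to say that censoring at death is inferred. If patients who died stayed in the risk set to Month 18, their deaths would not inflate 1-KM. The plan would still need to say so. Finally, deaths have their own analysis, and each biopsy-proven rejection, graft loss and death gets a narrative, so a large imbalance would not be hidden.

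**Conclusion.** The point holds as a minor one. The plan applies Kaplan-Meier to every component and gives no rule for death. Under the usual censoring, the reported rates of biopsy-proven rejection, rejection with hemodynamic compromise, graft loss, loss to follow-up, infarction and bypass exceed the proportions of patients who have those events.

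The size rests wholly on assumed rates: 0.02 to 1.44 points over the table, and at most k × d whatever the timing of deaths. For a 15% component with 2 to 5% deaths it is 0.15 to 0.37 points, against a confidence-interval half-width of 7.8 points.

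The composites do not have this bias from death, because death is an event in both. All-cause death and the log-rank tests also stand. A reader might infer that the comparison of rejection between arms is invalid; the documents and the calculation do not support that.

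**What to change.** In SAP 2.6.2, with the same change to Protocol 10.6.1:
- Keep Kaplan-Meier for the two composites and for death.
- Report the 12-month rate of each non-fatal component as cumulative incidence (Aalen-Johansen), with death as a competing event.
- For the two rejection components, add graft loss or re-transplantation as a competing event, dated when the original graft is actually no longer at risk, not when re-transplantation is scheduled or the patient is admitted.
- State that patients who only stop treatment stay at risk for as long as they are followed.
- Keep the log-rank test and label it a comparison of cause-specific hazards.

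The cost is a few sentences and a standard estimator. SAP 5.1.3 already names the sources for the dates of death and biopsy. The date on which the graft was replaced is not named there, but graft loss and re-transplantation must be reported on the serious adverse event form (Protocol 7.5), which is the place to look for it.

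The downside is that the reported rates and the log-rank p-value then describe different quantities. One sentence in the SAP should say so.
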